9. SAFETY EVALUATION

9.1 Overview of Safety Analysis Methods

The assessment of safety and tolerability is the secondary objective of this study. All safety analyses will be carried out using the Safety Population and will include the study eye and fellow eye separately, where applicable.

The assessment of safety will be evaluated by:

- Adverse events
- Heart rate and blood pressure
- Biomicroscopy of anterior segment including evaluation of cornea, conjunctiva and anterior chamber. (Fluorescein staining to be used.)
- Dilated ophthalmoscopy
- Best Corrected ETDRS Visual Acuity
- Visual fields
- IOP
- Clinical chemistry, hematology and urinalysis laboratory findings

All safety variables will be descriptively summarized by treatment group at each assessment time and for relevant changes from baseline.

For complete inclusion of subjects who withdraw from the study early, the End of Study visit for safety outcomes will be defined as either Visit 6 or Early Discontinuation.

9.2 Extent of Exposure

Summary statistics will be presented for treatment exposure. Note that date of first dose is not collected, but will be assumed to be the Visit 3 date. Treatment exposure will be defined as the number of days that the subject was exposed to study treatment as calculated using the formula:

$$\text{Treatment exposure} = \text{Date of Last Dose} - \text{Visit 3 Date} + 1.$$

9.3 Adverse Events

An adverse event is any untoward medical occurrence associated with the use of a drug in humans, whether or not considered drug related. All AEs occurring during the study (i.e. once the subject has received one dose of study drug) will be defined as treatment emergent adverse events (TEAEs) and must be documented, regardless of the assumption of causal relationship, on the respective AE CRF. All adverse events should be documented from the time the subject receives the first dose of study drug until the subject's participation in the study has been completed. If a subject has ongoing AEs at the time of study completion, the ongoing AEs must be followed-up and provided appropriate medical care until the event has resolved or stabilized. Documentation of AEs includes onset date, severity, action(s) taken, study medication relationship, outcome, resolution date, and seriousness.

Verbatim descriptions of AEs will be mapped to MedDRA, Version 20.0, thesaurus terms and be presented in a data listing. Ocular and non-ocular treatment emergent AEs, those that occur after the first dose of study medication, will be summarized by treatment group using frequencies and proportions for each system organ class (SOC) and preferred term (PT) within each SOC. Additionally, separate summaries will be presented for serious TEAEs, TEAEs that are related to the study drug (marked as “possibly related” or “related” in the CRF) and TEAEs resulting in study drug discontinuation. For these summaries, Fisher’s exact tests will be used to test the difference in proportions of subjects with each TEAE between treatment groups, SOC, and PT. Another table will be presented summarizing TEAEs by maximum severity.

An overall summary table will be developed to report the number of events and the incidence of subjects having at least one event in the following categories:

- TEAEs
- Ocular TEAEs
- Non-Ocular TEAEs
- Serious TEAEs (SAEs)
- Treatment-Related TEAEs (reported as possibly related or related to the study drug)
- Treatment-Related SAEs
- TEAEs by severity
- TEAEs leading to study drug discontinuation
- TEAEs resulting in death

While the overall summary of TEAEs will present both the number of TEAEs and the incidence of TEAEs, the other summaries will only report the incidence of TEAEs. When reporting the number of TEAEs, if the same TEAE occurs for a subject on multiple occasions the event will be counted once for each occurrence. When reporting the incidence, a subject will only be counted once if they ever experience an event within the SOC and ever experience the individual PT. Summaries will be performed using the actual treatment received.

9.4 Deaths, Serious Adverse Events, and Other Significant Adverse Events

An adverse event is considered “serious” if, in the view of either the Investigator or Sponsor, it results in any of the following outcomes: Death, a life-threatening or sight-threatening adverse event, inpatient hospitalization or prolongation of existing hospitalization, a persistent or significant incapacity or substantial disruption of the ability to conduct normal life functions, or a congenital anomaly/birth defect. Serious adverse events and deaths will be listed and summarized separately for the Safety population.

9.5 Clinical Laboratory Evaluation

Clinical laboratory results, including clinical chemistry, hematology and urinalysis, will be presented in data listings. Abnormal results, those above or below the normal range, will be flagged with "H" (high), “HP” (high panic), "L" (low), “LP” (low panic) or “AB” (abnormal) based on the laboratory ranges provided by the lab and included in the listings. Descriptive statistics will be used to summarize continuous measures and will be presented in tabular form

including change from baseline to the Week 4 visit. Shifts from baseline to the Week 4 visit will also be presented in tabular form for clinical chemistries, hematology and urinalysis parameters by treatment group and laboratory domain. Summary tables also will be presented for the number of subjects with abnormal values within each laboratory parameter at the end of the study. Clinical laboratory results, including clinical chemistry, hematology, urinalysis and urine pregnancy test will also be listed by subject.

9.6 Vital Signs, Ophthalmic Exam Findings, and Other Safety Outcomes

9.6.1 Vital Signs

Heart rate and blood pressure will be listed by treatment group, subject, and visit including observed values and changes from baseline. Measurements and change from baseline measurements will be summarized by treatment group and visit. Paired t-tests will be used to test within treatment group changes from baseline in vital sign parameters. Two-sided 95% CIs will be provided.

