6.8 Safety Assessments

The primary safety measures in both eyes of enrolled subjects will include:

- Ocular symptoms/adverse events

- Best corrected visual acuity
- Objective findings of biomicroscopic examinations (i.e., anterior segment examinations including evaluation of cornea, conjunctiva, lids, and lens)
- Dilated ophthalmoscopy, including vertical cup-disc ratio measurements

Other safety assessments will be:

- Systemic safety assessments as measured by heart rate, blood pressure, and clinical laboratory evaluations (including hematology, clinical chemistry, and urinalysis)
- Pregnancy testing (for women of child bearing potential)

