9.7 Safety

9.7.1 Safety Endpoints

- Ocular symptoms/adverse events
- Best corrected visual acuity
- Objective findings of biomicroscopic examinations (i.e., anterior segment examinations including evaluation of cornea, conjunctiva, lids, and lens)
- Dilated ophthalmoscopy, including vertical cup-disc ratio measurements

Other safety assessments will be:

- Systemic safety assessments as measured by heart rate, blood pressure, and clinical laboratory evaluations (including hematology, clinical chemistry, and urinalysis)
- Pregnancy testing (for women of child bearing potential)

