9.7.2 Safety Analyses

Verbatim descriptions of AEs will be mapped to MedDRA thesaurus terms and be presented in a data listing. Treatment emergent AEs, those that occur after the first dose of study medication, will be summarized by treatment group using frequency and percent for each system organ class (SOC) and preferred term (PT) within each SOC. Summaries will be presented separately for ocular and non-ocular AEs. These summaries will also be presented for relation to Investigational Product and by severity. Fisher's exact test will be used to test the difference in proportions of subjects with each AE between treatment groups netarsudil (0.02% or 0.04%) vs placebo.

Visual acuity data will be summarized at each time point using both continuous summaries (logMAR), including change from baseline, and discrete summaries, including change from baseline on an ETDRS chart (or equivalent) in the number of lines and the proportion of subjects with a worsening of ≥ 3 lines from baseline.

Slit lamp biomicroscopy and dilated ophthalmoscopy measures will be summarized at each measured time point using discrete summary statistics. Conjunctival hyperemia will also be summarized using continuous summary statistics including change from baseline and change from baseline (pre-washout).

Visual field mean deviation and vertical cup-to-disc ratio will be summarized at each visit and for change from baseline to each visit using continuous summary statistics by treatment group and visit.

Vital signs will be summarized at each visit and for change from baseline to each visit using continuous summary statistics by treatment group and visit.

Clinical laboratory results will be summarized using both continuous summaries, including change from baseline, and discrete summaries, including frequency and percent of subjects with an abnormal value and shift tables from baseline. Additionally, laboratory data will be presented in data listings. A copy of the certification and a table of the normal ranges for the reference laboratory conducting any clinical laboratory tests required by this protocol must be provided.

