2. PROTOCOL SUMMARY

2.1 Study Objectives

The primary objectives of this study are to evaluate:

- The ocular hypotensive efficacy of netarsudil ophthalmic solution relative to its placebo over a 28-day period
- The ocular and systemic safety of netarsudil ophthalmic solution relative to its placebo over a 28-day period

The secondary objectives of this study are to evaluate:

None.

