For each qualification visit, individuals who do not meet the IOP requirement may return for up to 2 additional unscheduled qualification visits within 1 week of failing the specific qualification visit. Individuals returning at an unscheduled visit within 1 week are required to only re-measure IOP in both eyes. Upon return, such individuals would need to qualify at 08:00, 10:00 and 16:00

hours to continue the study. Individuals who fail due to IOP being ≥ 35 mmHg in either eye (exclusion criterion) MAY NOT return for additional qualification visits.

At this point, eligible subjects will be enrolled and assigned to an investigational product through an IWRS according to a computer-generated randomization list. The study medication kit containing 2 bottles will be dispensed through the IWRS to the eligible subject, along with dosing and storage instructions.

For each subject, both eyes will be treated. Subjects will be:

- Instructed to self-administer their masked medication at home between 20:00-22:00 hours (8 PM - 10 PM) beginning with the evening dose on that day

Subjects will return for post-treatment Visits 4.0, 4.1, and 4.2 (Week 1 [Day 8]; 08:00, 10:00, and 16:00 hours), Visits 5.0, 5.1, and 5.2 (Week 2 [Day 15]; 08:00, 10:00, and 16:00 hours), Visits 6.0, 6.1, and 6.2 (Week 4 [Day 29]; 08:00, 10:00, and 16:00 hours).

Symptomatology/adverse events (AE), review of concomitant medications and non-dilated eye examinations including IOP and biomicroscopy will be conducted at all of these visits. Vital signs and BCVA will also be conducted at Visits 4.0, 5.0 and 6.0. Any symptoms reported, or clinical signs observed which have worsened, either from baseline or from previous visits at these post-dose visits, will be recorded as treatment emergent adverse events (TEAE). At Visit 6 (Week 4 [Day 29]), a urine pregnancy test (for women of child-bearing potential) will be performed and blood will be drawn for clinical labs. A dilated ophthalmoscopy will be performed at Visit 6.2 (Week 4 [Day 29], 16:00 hours).

A study schedule of events table is presented in Appendix 1.

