Due to the early study closure, the sample size is expected to be approximately 10 ITT subjects per arm. The study will not be able to achieve the adequate power for primary hypotheses as planned. Therefore, the analyses will be performed based upon the observed data for informational purposes only. No statistical inference will be made. No subgroup analyses will be performed.

There will be no adjustment for the multiplicity of the 2 active concentrations (0.02% and 0.04%) tested against placebo in this Phase 2 study.

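### The only tests the SAP names for heart rate and blood pressure are of change within each arm, which do not address systemic safety relative to placebo; the effect is modest and cheap to put right

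*SAP*

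**What the plan says.** Protocol 2.1 and SAP 2.1 both list as a primary objective "The ocular and systemic safety of netarsudil ophthalmic solution relative to its placebo over a 28-day period". Protocol 9.7.1 names the systemic measures: "Systemic safety assessments as measured by heart rate, blood pressure, and clinical laboratory evaluations". Both there and in Protocol 6.8 they come after the primary safety measures, in a list introduced by "Other safety assessments will be".

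Protocol 9.7.2 plans description only: "Vital signs will be summarized at each visit and for change from baseline to each visit using continuous summary statistics", by treatment group and visit. It names no test for vital signs.

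SAP 9.6.1 keeps the description: "Measurements and change from baseline measurements will be summarized by treatment group and visit". It then adds inference: "Paired t-tests will be used to test within treatment group changes from baseline in vital sign parameters". A further sentence promises two-sided 95% intervals without saying what they estimate. SAP 13, on changes from the protocol, speaks only of efficacy and does not mention the added tests.

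On timing, SAP 2.2 says "Vital signs and BCVA will also be conducted at Visits 4.0, 5.0 and 6.0". SAP 8.1.2 and 9.1 combine early-termination and end-of-study data for safety, so the last safety visit is Visit 6 or Early Discontinuation.

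**The concern.** A paired t-test within a netarsudil arm asks whether that arm's mean change from baseline is zero. That change is any drug effect plus whatever moves all arms alike, such as regression to the mean or familiarity with the visits. The placebo arm is there to remove the shared part, and a within-arm test does not use it.

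The risk is in the reading. If all arms drift by the same amount, a netarsudil arm may reach significance while placebo, by chance, does not. A table showing that pattern invites the conclusion that the drug changed heart rate or blood pressure. Meanwhile the quantity that bears on the objective, the netarsudil minus placebo difference with its interval, would have to be assembled by the reader from the by-arm summaries.

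**Working it through.** **Inputs.** Two-sided level 0.05 (SAP 3). Three arms, randomized 1:1:1 (SAP 2.5). After early closure, "the sample size is expected to be approximately 10 ITT subjects per arm" (SAP 8.2), so n = 10. The documents give no SD, expected change or power figure for vital signs, and the sample-size section concerns IOP only, so there is no stated figure to reproduce. I therefore assume a shift d common to all arms, in SD units of the change score, with no drug effect and independent, normally distributed arms.

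**Step 1: one paired test.** The statistic is noncentral t with 9 degrees of freedom and noncentrality d × √10. Its probability of significance is p.

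**Step 2: the pattern open to misreading.** At least one of the two netarsudil arms is significant and placebo is not, with probability (1 − p) × [1 − (1 − p)²]. At d = 0.5, for example: 0.707 × (1 − 0.707²) = 0.707 × 0.500 = 0.354.

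| Common shift d | p, one arm | Netarsudil significant, placebo not |
|---|---|---|
| 0 | 0.050 | 0.093 |
| 0.25 | 0.109 | 0.184 |
| 0.5 | 0.293 | 0.354 |
| 0.75 | 0.562 | 0.354 |
| 1.0 | 0.803 | 0.189 |

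The probability rises and then falls: with a large shared shift, placebo usually becomes significant too. All figures are per parameter and visit.

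**Step 3: the like-for-like comparison.** In a direct netarsudil minus placebo comparison the common shift cancels, so the rejection rate does not depend on d. It is 0.05 per comparison. By simulation, the chance that at least one of two unadjusted comparisons is significant is about 0.09, whether by two-sample t on change or by three-arm ANCOVA. At d = 0 the two approaches therefore carry the same risk (0.09 each).

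**Step 4: precision of the direct comparison.** 95% half-widths, in SD of the change score:

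- Two arms, unadjusted: t(0.975, 18) × √(2/10) = 2.101 × 0.447 = 0.94.
- Variance pooled over three arms, unadjusted: t(0.975, 27) × √(2/10) = 2.052 × 0.447 = 0.92.
- Three-arm ANCOVA, simulated mean for an assumed baseline to follow-up correlation of 0.3, 0.5 or 0.7 with equal variances: about 0.75, 0.80 or 0.86.

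The fair reference for ANCOVA is 0.92, since the step from 0.94 to 0.92 comes only from the pooled degrees of freedom.

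**Step 5: volume of output.** Assuming heart rate, systolic and diastolic pressure at three visits, the paired plan gives 3 × 3 × 3 = 27 p-values. Two contrasts against placebo give 3 × 3 × 2 = 18 estimates.

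**The case against.** The best defence is that the comparison with placebo is not lost. SAP 9.1 and 9.6.1 summarize values and changes by arm, placebo included, which is what the protocol planned. The paired tests are valid for the null they test. Vital signs are among the other safety assessments, no decision depends on their p-values, and neither document tells anyone to read significance in one arm and not another as a drug effect. All of this stands, and it is why the point is small.

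The SAP's statements that no statistical inference will be made are less help. They appear in its efficacy sections and in SAP 13, which concerns the efficacy analyses, while 9.6.1 still calls for tests.

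Four stronger readings are tempting, and the documents do not support them:

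- **That vital signs are singled out while other safety data are compared with placebo.** Between-group tests are planned for adverse events (SAP 9.3) and biomicroscopy, including conjunctival hyperemia (SAP 9.6.5). Laboratory results (9.5), safety IOP (9.6.2), visual acuity (9.6.3) and ophthalmoscopy (9.6.4) have none. What is peculiar to 9.6.1 is the added within-arm test.
- **That the report will contain no vital-sign comparison with placebo.** The table shells are attachments outside the public text, and SAP 1 and 11 allow further analyses. One can say only that the visible text names none.
- **That the 95% intervals are certainly within-arm.** Their position suggests it, but the SAP does not say.
- **That the paired tests have an inflated error rate.** The probabilities above become errors only if the pattern is misread as a drug effect.

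**Conclusion.** The mismatch holds: the only vital-sign tests named in the visible text answer whether each arm changed, while the objective asks whether netarsudil differs from placebo. It is a modest defect, worth correcting but not one that threatens the trial's conclusions.

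Its size depends on a shared shift that the documents do not give. Over an assumed 0 to 1.0 SD, the chance of the misleading pattern runs from 0.09 to a peak of about 0.35 and back to 0.19, against a constant 0.09 or so for direct comparisons. With no shared shift there is no disadvantage. Confidence is high on what SAP 9.6.1 says and lower on what the final tables will show.

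**What to change.** In SAP 9.6.1, replace the paired t-tests with two estimates per parameter and visit: netarsudil 0.02% minus placebo and netarsudil 0.04% minus placebo. Use either ANCOVA with the baseline value as covariate or a two-sample comparison of change from baseline. The latter is closer to the SAP's own precedent for hyperemia. Report them at Week 1, Week 2 and the End of Study visit, defined as Visit 6 or Early Discontinuation as in SAP 8.1.2 and 9.1. Naming Visit 6.0 alone would drop early-termination vital signs. State that the 95% CIs are for these differences and are descriptive. Keep the by-arm summaries.

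The cost is two SAP sentences and a small program change on data already collected. The drawback is wide intervals: at about 10 per arm only large differences could be excluded. That limit is a fact about the sample and is better shown than hidden.

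The minimum alternative is to drop the paired tests and keep the descriptive plan of Protocol 9.7.2. If any interval is then retained, the SAP should say what it estimates.

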9.6.2 Intraocular Pressure

Intraocular pressure will be presented in data listings. Intraocular pressure data will be summarized at each visit and time point using continuous summaries, including change from baseline, for both the study eye and the fellow eye.

9.6.3 Visual Acuity

Visual acuity scores will be presented in data listings. Subjects who lost three or more lines will be presented in an additional listing. Visual acuity data will be summarized at each visit using continuous summaries, including change from baseline, for both the study eye and the fellow eye. Additionally, discrete summaries of the worst change from baseline will be presented for both the study eye and the fellow eye with the following groupings based on the logMAR scores: 0 or less, >0 to +0.09, +0.10 to +0.19, +0.20 to 0.29, +0.30 or more.

9.6.4 Dilated Ophthalmoscopy and Cup-to-Disc Ratio

Dilated ophthalmoscopy and cup-to-disc ratio results from Screening and Week 4 visits will be presented in data listings. A separate listing will be created for those subjects with a criterion change, defined as a change from “Normal” to “Abnormal” or a change from “Abnormal – Not Clinically Significant” to “Abnormal – Clinically Significant”. Frequencies and percentages of normal, abnormal – not clinically significant, and abnormal – clinically significant ophthalmoscopy results will be created for the following fields: Retina, Macula, Choroid, Optic Nerve, and Vitreous Humor. Abnormal results will further be broken down by clinical significance. A shift table of study eye and fellow eye ophthalmoscopy results will also be presented by treatment group.

Vertical cup-to-disc ratio at Screening will be summarized for the study eye and for the fellow eye by treatment group in the baseline characteristics table. Additionally, vertical cup-to-disc ratio will be summarized at Week 4 visit and change from baseline to Week 4 visit using

continuous summary statistics. A listing of subjects with increases of ≥ 0.2 in either eye at end of study will be presented.

9.6.5 Biomicroscopy

Biomicroscopy results will be listed for both eyes at each visit and time point. A separate listing will be presented for subjects with a criterion change, defined as a +1 unit increase from baseline. Summaries of biomicroscopy results will also be presented for study eyes and fellow eyes by treatment group, visit, and time point in tabular form.

A summary table of the number and percentage of subjects with at least a +1 unit increase in score from baseline will be presented by region, finding, time point and eye (study eye and fellow eye). In addition to each time point, there will be summaries for “At the Final Visit” and “At Any Visit”.

Another summary table will be presented with the number and percentage of subjects who had a finding judged to be clinically significant by region, finding, time point and eye (study eye and fellow eye). Fisher’s exact tests will be used to compare incidence between treatment groups in both tables. Additionally, Conjunctival Hyperemia will be presented using continuous summary statistics for each visit, for the change from baseline to each post-baseline visit. Differences between treatment groups will be tested using two-sample t-tests as well as Wilcoxon rank sum tests.

